## Adverse Event and Serious Adverse Event

Interim analyses. Two interim analyses will be performed, once 50 subjects and 100 subjects complete the study. The main goal of the interim analyses will be monitoring of patient safety. The anticipated possible adverse events fall into two categories: adverse events related to the study sensor and adverse events related to heart failure therapy.

Interim analysis of adverse events related to the study sensor. We will report to the DSMB the rate of AEs related to the study sensor. We anticipate these may include local allergic reaction to the adhesive, skin rash or skin abrasion. While not reported previously, systemic allergic reaction to the adhesive could also occur.

Interim analysis of adverse events related to heart failure therapy. The study intervention is expected to improve clinical outcomes in subjects with heart failure. However, since the algorithmic response triggered by a study alert calls for changes in heart failure therapy or changes in follow-up, there could be adverse events related to these changes triggered by study procedures.

The following events will be recorded, adjudicated and reported to the data coordinating center: - Over diuresis

- Hypotension induced by heart failure medications
- Other adverse events attributed to HF therapy
- Hospitalization

Reporting of interim analyses. The data coordinating center will tabulate the rates of adverse events at the time of the interim analyses.

Adverse events related to the study sensor will be presented for all study subjects, since all study subjects will wear the sensor regardless of randomization assignment. Adverse events related to

heart failure therapy will be tabulated by randomization assignment. This information will be generated by the data coordinating center and provided to the DSMB. The detailed data by randomization group will not be shared with study investigators unless a protocol modification is deemed necessary by the DSMB.

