An Adverse Event is any undesirable experience (as judged by the principal investigator) associated with the use of a medical product in a subject that is not judged to be serious. The event will be deemed a Serious Adverse Event and should be reported to the IRB as such when the subject outcome is: Death, Life-threatening, Hospitalization (initial or prolonged), Disability or Permanent Damage, Required Intervention to Prevent Permanent Impairment, or other serious events as judged by the principal investigator. (See for reference FDA definition at:

<http://www.fda.gov/Safety/MedWatch/HowToReport/ucm053087.htm>)

All events shall be reported as per institutional guidelines.

Medical record request to non-VA hospital or emergency department or clinic

In the event that an acute care episode (a primary event) occurs at a non-VA facility, medical records will likely be provided to the clinical team. In the unlikely situation that this does not take place, the subject will be asked to sign a medical record release form, and the study team will obtain the records in question. Relevant data will be entered into the electronic case report system. A subject may also sign the medical record release at the time of consent to cover any possible outside admissions during enrollment.

Determination of Exacerbation timing/Cause

In the event that an acute care episode (a primary event) occurs and is determined to be an exacerbation of a subject's chronic conditions, the site PI will make a determination of the timing and cause of the exacerbation.

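### The adverse event definition excludes serious events, so serious sensor reactions and some other serious events have no stated place in the interim safety tables

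*Combined protocol and SAP*

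**What the plan says.** The relevant text is in the combined protocol and SAP, section 6.0 Reporting, under Adverse Event and Serious Adverse Event.

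**Definitions.** The principal investigator decides what counts as undesirable, and an adverse event is an experience of that kind "associated with the use of a medical product in a subject that is not judged to be serious". A further sentence then turns to seriousness: "The event will be deemed a Serious Adverse Event and should be reported to the IRB as such when the subject outcome is" one of a list of outcomes. The list covers death, threat to life, hospitalization, disability, intervention needed to prevent permanent impairment, and anything else the investigator judges serious. A closing sentence sends all events through institutional guidelines.

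**Interim analyses.** Two are planned, after 50 and after 100 subjects complete, and their main stated purpose is patient safety.

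- For the sensor: "We will report to the DSMB the rate of AEs related to the study sensor". Local allergic reaction, rash and abrasion are expected. The text adds that, although not reported before, "systemic allergic reaction to the adhesive could also occur".
- For HF therapy: "The following events will be recorded, adjudicated and reported to the data coordinating center". The list that follows has four items: over diuresis, hypotension caused by HF medication, a residual category of other adverse events put down to HF therapy, and "Hospitalization".

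The data coordinating center tabulates adverse event rates for the DSMB, with sensor events shown for all subjects together and HF-therapy events by randomized arm. Neither the interim text nor the Data Monitoring section specifies a table of SAEs or deaths.

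**The concern.** A safety table should contain the serious events, because these matter most to a board deciding whether a trial may continue unchanged. Here the definition makes AE and SAE separate categories, while the interim outputs are worded as rates of AEs. Whoever programs the sensor table from the written definition would leave out a reaction that threatened life or needed intervention to prevent permanent harm. That is the type of sensor event on which the board would most want information.

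The text also conflicts with itself. Hospitalization appears among the events for the adverse event tables, but under the definitions it makes an event serious and therefore not an AE. Both statements cannot hold, and the plan does not say which governs.

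**Working it through.** No arithmetic applies. The documents give no AE or SAE rate, no safety threshold and no stopping boundary, so there is no figure to reproduce. The check sets the definitions beside the interim text and asks, for each kind of serious event, whether the plan gives it a place in an interim table.

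**Step 1: what the definition excludes.** Read literally, once an event is judged serious it is no longer an AE. A table whose content is the rate of AEs then holds non-serious events only.

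**Step 2: sensor table.** Its only stated content is the rate of sensor-related AEs, and it has no serious category. A local rash is in. A systemic allergic reaction that meets none of the listed outcomes is in. The same reaction, if life-threatening or needing intervention to prevent permanent impairment, is out. If it led to admission it could at most be counted on the hospitalization line of the HF-therapy list, where nothing would identify it as a sensor event. The gap therefore exists for every serious sensor reaction.

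**Step 3: HF-therapy table.** The four listed items behave differently.

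| Listed item | Limited to non-serious events? | Serious cases captured? |
|---|---|---|
| Over diuresis | No severity limit stated | Yes, by name |
| Hypotension from HF medication | No severity limit stated | Yes, by name |
| Other adverse events put down to HF therapy | Yes, because it uses the defined term | Not if managed without admission |
| Hospitalization | No, it is itself a criterion for seriousness | Yes, by name |

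Only one of the four items takes on the narrow definition. Serious cases in that category that lead to admission still reach the table through the hospitalization line.

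**Step 4: deaths.** Death is among the listed serious outcomes but is not an item in either interim table. A death preceded by an admission is represented by that admission. A death without one has no stated place as a death.

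**Step 5: other routes to the DSMB.** The Data Monitoring section provides for DSMB oversight about every 6 months and says that investigators supply the data requested and summary reports. The content of those reports is not specified. The institutional-guidelines sentence names neither the DSMB nor the interim tables. The Status and Event Questionnaire triggers AE/SAE evaluations, which shows that serious events are to be assessed, but does not say where they are tabulated. None of these commits the plan to showing SAEs at the interim analyses.

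**The case against.** The strongest reply is that this is loose drafting with an inclusive intent. The section heading covers both AEs and SAEs. The interim text places hospitalization and possible systemic reaction among adverse events, so it appears to use the term in the ordinary broad sense. The SAE sentence begins with a reference back to the event just described, which can be read as reclassifying an AE by its outcome. The plan nowhere states that serious events are to be left out of the interim tables, and the DSMB may request any data it wants. The sensor reactions that are expected are mild, and systemic reaction is described as not previously reported, so few events may be affected.

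Most of this stands as evidence of intent. It does not repair the definition. If the intent is inclusive, the definition says the opposite and should be corrected, because the tables will be built from the written text.

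A reader might infer several stronger conclusions that the documents do not support:

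- *The most severe events drop out of both tables.* This fails for HF therapy, where a serious hypotensive episode or an over diuresis event is captured by name and hospitalization is listed outright.
- *The DSMB will not see serious harm.* The request and summary-report route may show SAEs; the plan simply does not commit to it.
- *The reported rate will be too low by a stated amount.* Any such figure would rest on invented event counts, and there is no threshold against which it would change a decision.
- *Published AE rates will carry the same error.* The documents contain no plan for publishing AE rates.
- *Sensor events should also be split by arm.* The plan pools them because both arms wear the sensor, and nothing in the definition problem calls for a change.

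**Conclusion.** The point holds as a wrong definition that conflicts with the plan's own interim text. Its reach is limited to three groups: all serious sensor reactions, serious events in the residual HF-therapy category handled without admission, and deaths without admission. The conclusion rests on reading the AE definition as written and on no other specified output filling the gap. On an inclusive reading nothing would be lost, but that reading contradicts the definition. The number of events affected cannot be derived from the documents and may be small. The correction is still worth making, because the interim analyses exist mainly for patient safety and the affected events are the gravest of their kind.

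**What to change.** In the definitions, describe an adverse event as any undesirable experience, and a serious adverse event as an AE that meets one of the outcomes already listed. Leave the IRB reporting route unchanged.

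In the interim analysis text, state that the tables given to the DSMB show all AEs, split into serious and non-serious, and that deaths are included. Keep sensor events pooled across arms as planned and HF-therapy events by randomized arm.

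The cost is a few sentences of protocol wording and one more column in the interim tables. The protocol already provides for AE/SAE evaluation of reported events, and no clinical rule changes. It should be in place before the tables for the first interim analysis are programmed.

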### **Inventory of Procedures/ Tests on Readmission**

In the event that a primary event occurs, the PI will have made an inventory of acute care interventions and diagnostic tests carried out on the subjects, as well as length of stay,

### **Study Discontinuation**

Insufficient or poor-quality data

If subjects opt not to wear the device, or if the telemonitoring data are of poor quality, the study team may decide to discontinue the subject from the study.

### **Definition of Medical Events**

Primary Events

1. The proportion of randomized patients who meet the algorithm's criteria for at least one alert;
2. The ratio of the number of days the remote monitor is functioning properly (patient wearing device and data quality sufficient to make the daily decision) to the total number of days in the study;
3. The rate of HF hospitalization, all-cause hospitalization and LOS for those hospitalized;

#### Additional Event Characterizations

For each of the above primary and secondary events, additional details will be captured to relate them to disease and to identify the window for precursor detection and the impact of the event:

1. HF-related or not
2. Exacerbation or not
3. Date of intervention
4. Onset date of first symptoms (if reported)
5. Date and nature of trigger/cause for event, as assessed by PI (if possible)
6. Intervention performed
7. Diagnostic tests performed
8. Outcome of intervention
9. Length of hospital stay

### **DATA MONITORING**

All study patient data will be stored both on paper and electronically on secured, password-protected computer systems in physically locked facilities at the VA and at PhysiQ offices. The only people who will have authorized access to any of this data are the investigative medical staff at the VA hospital, and authorized personnel of PhysiQ, all of whom have been certified under patient confidentiality training.

All centers will use eCRF's-OpenClinica. All research staff having access to study data have completed the VA Privacy and HIPAA training and the VA Privacy and Information Security Awareness and Rules of Behavior training within the past twelve months which will be locked at all times with access available only to the investigator team. Data regarding adverse events will be sent to PhysiQ. All other data will be completed via eCRF. Queries will be issued by PhysiQ for non-conformant/incomplete data. The VA Health Services Research and Development Office will provide oversight in the form of an Data Safety and Monitoring Board (DSMB).

The Data Safety and Monitoring Board (DSMB) is convened by the HSR&D VA office in Washington, DC. and will provide data monitoring oversight to the study approximately every 6 months.

The investigators will provide the requested data and summary reports to the DSMB. Then the DSMB will summarize their findings in letters provided back to the site.

## 7.0 Privacy and Confidentiality

### HIPAA Release Form

All study patient data will be stored both on paper and electronically on secured, password-protected computer systems in physically locked facilities at the VA and at PhysIQ offices. The only people who will have authorized access to any of this data are the investigative medical staff at the VA hospital, and authorized personnel of PhysIQ, all of whom have been certified under patient confidentiality training.

Data collection outlined in the protocol will be collected on electronic case report forms (eCRFs in OpenClinica. OpenClinica is a HIPAA compliant cloud-based data reporting system commonly used in multi-center clinical trials).

All research staff having access to study data have completed the VA Privacy and HIPAA training and the VA Privacy and Information Security Awareness and Rules of Behavior training within the past twelve months which will be locked at all times with access available only to the investigator team.

The implementation and qualitative research study procedures and recorded interviews will be in safeguarded on password protected computers.

- [name] will maintain seamless communication with PhysIQ, the industry partner providing remote monitoring hardware and software, participating in site startup, clinical personnel training and serving as data coordinating center. [name] will assure that all the study procedures outlined in the study plan proceed as expected and according to the established timeline. PhysIQ was an industry partner in the pilot LINK-HF study funded by the VA Center for Innovation - this collaboration was successful, and no issues of concern were identified.
- The study team will participate in conference calls and investigator meetings. The Principal Investigators will communicate with the study team at least quarterly through conference calls to discuss study progress, any difficulties in following study procedures and any adverse events. Additionally, we plan one in-person investigator meeting. Any decisions involving possible need for changes in study procedures or any other modifications to the research approach will be discussed during investigator calls and input from all the PIs will be sought.
- [name], project manager at the SLC VAMC will ensure that regulatory approval at all the 6 participating sites is maintained and communicate closely with local study coordinators. [name] will monitor progress of approvals of any amendments to the protocol.

